# 6.1.3 X-ray Imaging

Disc height, intervertebral posterior angle, and translation of vertebral body will be assessed by X-ray in accordance with the schedule of assessments Table 3.

The following will be reported as AEs:

- a decrease in disc height  $\geq 30\%$  compared to baseline
- vertebral body angle formed by flexion of  $\geq 5^{\circ}$
- vertebral body translation of  $\geq 3 \text{ mm}$

Events are limited to the targeted level of the investigational drug administration and the adjacent vertebral bodies (see Appendix 11.7).

Anteroposterior and lateral-intermediate, flexion, and extension spinal x-rays will be obtained according to the "*Procedure Manual for Radiographic Examinations of the Lumbar Spine*". The X-ray images obtained will be sent to the central imaging reader (BioClinica) for assessment.

#### 6.1.3.1 Disc Height (Disc Index)

The central imaging reader will measure the disc index for the intervertebral disc treated with the investigational drug using

- a) the posterior height of the superior vertebral body adjacent to the target segment,
- b) the anterior disc space, and
- c) the posterior disc space.

A decrease in disc height  $\geq$ 30% compared to baseline value will be recorded as an AE (see Appendix 11.7 for additional details regarding imaging tests).

#### 6.1.3.2 Intervertebral Posterior Angle

The central imaging reader will measure the intervertebral posterior angle of the intervertebral disc treated with the investigational drug. When the measured value is  $\leq$ -5°, the relevant result will be entered as "posterior intervertebral angulation" in the eCRF. A vertebral body angle formed by flexion of  $\geq$ 5° will be recorded as an AE (see Appendix 11.7 for details regarding imaging tests).

#### 6.1.3.3 Vertebral Body Translation

The central imaging reader will determine the difference in vertebral body translation at the extension and flexion positions of the intervertebral disc treated with the investigational drug. When the post-treatment vertebral body translation is  $\geq 3$  mm, the relevant result will be entered as "vertebral body translation" in the eCRF. A vertebral body translation of  $\geq 3$  mm will be recorded as an AE (see Appendix 11.7 for details regarding imaging tests).

#### 6.1.4 Magnetic Resonance Imaging

Changes of disc degeneration, vertebral body endplates, and adjacent bone marrow will be assessed by MRI in accordance with the schedule of assessments Table 3.

The criteria are as follows: Modic Type 1, Type 2, or Type 3 change in vertebral body endplates and adjacent bone marrow (see Appendix 11.5) and Grade I (mild), Grade II (moderate), or Grade III (severe) in disc degeneration using Pfirrmann classification (see Appendix 11.6). When the post-treatment Modic Type 1, Type 2, or Type 3 change in vertebral body endplates and adjacent bone marrow occur, the relevant result will be entered as "Modic Type 1", "Modic Type 2" or "Modic Type 3" in the eCRF. Modic Type 1, Type 2, or Type 3 change in vertebral body endplates and adjacent body endplates and adjacent bone marrow occur, the relevant result will be entered as "Modic Type 1", "Modic Type 2" or "Modic Type 3" in the eCRF. Modic Type 1, Type 2, or Type 3 change in vertebral body endplates and adjacent bone marrow will be reported as an AE.

The MRI will be obtained according to the "*Procedure Manual for MRI Examination*". All MRIs obtained will be sent to the central imaging reader (BioClinica) for assessment.

#### 6.1.5 Vital Signs

The following vital signs will be assessed in accordance the schedule of assessments Table 3:

- Blood pressure (systolic and diastolic; mmHg) after being supine for 5 minutes
- Heart rate (beats per minute)
- Body temperature (°F/C)

• Respiration rate (breaths per minute)

#### 6.1.6 *Physical Examinations*

Physical examinations will be performed in accordance with the schedule of assessments Table 3. The physical examination should include evaluation of the skin, head, neck, throat, ears, eyes, nose, heart, lungs, abdomen, extremities, and musculoskeletal systems.

#### 6.1.7 Neurological Examinations and Pain Assessments

Neurological examinations and pain assessments will be performed in accordance with the schedule of assessments Table 3.

Neurological testing will include an FNS or SLR test, sensation, muscle strength, and deep tendon reflex. Any neurological finding that worsens after the administration of the investigational drug and that is considered to be clinically significant in the Investigator's judgment meets AE reporting criteria.

Cases where leg pain or back pain increase over the Screening period (baseline value) and, in the Investigator's judgment, is clinically aggravated, meet AE reporting criteria. Cases considered clinically exacerbated, in the Investigator's judgment, based on post treatment improvement followed by the reappearance of pain of equal severity than before improvement meet AE reporting criteria.

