- 8. Patients with the following medical conditions or diseases:
  - Vertebral body angle formed by flexion  $\geq 5^{\circ}$
  - Neurological disorders including cauda equina syndrome that is severe or that demonstrates rapid progression. Patient with clinically symptomatic neurological deficit (e.g., motor paresis, sphincter dysfunction), warranting an alternative option of care that would be more appropriate for their presentation, will be also excluded.
  - Spondylosis deformans, spondylolisthesis (translation of vertebral body ≥3 mm), spinal deformity, spinal canal stenosis (except for complication of lumbar disc herniation), spinal tumor, ankylosing spondylitis, diskitis, or clinically significant disorders of the lumbar spine other than disc herniation.
  - Osteophyte at lumbar spine (Nathan's classification  $\geq$  3rd degree)
  - Cancer: patients who have cancer or a past history of any cancer within 5 years prior to the time of informed consent, with the exception of basal cell or squamous cell carcinoma of the skin curatively treated or localized gynecologic cancer treated by total hysterectomy.
  - Human immunodeficiency virus (HIV) infection or a clinically significant infection
  - A clinically significant disorder such as cerebrovascular disease, pulmonary infarction, ischemic heart disease, cardiac dysrhythmia, myocardial infarction, or congestive heart failure
  - Chronic diseases such as osteoporosis, rheumatoid arthritis, uncontrolled diabetes mellitus, uncontrolled pulmonary disease (asthma), or uncontrolled hypertension
  - Patients who have evidence of major psychiatric disease, mental disorder, drug dependency, alcohol dependency, or substance use disorders.
  - Patients who have a tendency to bleed or with bleeding disorders such as (but not limited to) hemophilia, hypoplastic anemia, cirrhosis of the liver, leukemia and vitamin K deficiency. Patients using medication for purpose of anticoagulation, including heparin and warfarin which cannot be reversed preoperatively will also be excluded.
- 9. Patients with medical conditions and/or diseases that the Investigator believes could affect the study results or the safe conduct of the study.
- 10. Patients who meet any of the following criteria:

- Hepatic function: AST or ALT:  $\geq 2.5$  x upper limit of normal (ULN)
- Total-bilirubin:  $\geq 1.5 \text{ x ULN}$
- Renal function: Serum creatinine:  $\geq 1.5 \text{ x ULN}$

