#### 7 STUDY CONDUCT

#### 7.1 Schedule of Procedures

Each patient will be asked to complete 6 study visits including a screening evaluation:

- Screening visit
- Treatment Day 0
- Evaluation period/Follow-up visits at Week 1, Week 6, Week 13, and Week 26
- Patients terminating the study early will be asked to complete a discontinuation visit.

Table 3:         Schedule of Assessments and Procedures								
Observation Period	Before 4 Weeks (Day -28 to Day 0)	Treatment	Day 0	Week 1	Week 6	Week 13	Week 26	Upon Discontinuation
	Outpatient a							Upon Disc
Observation / Examination Items	Screening Period	Evaluation Period/ Evaluation Period/ Follow-up						
	Visit 1	Visi	it 2	Visit 3	Visit 4	Visit 5	Visit 6	
Permissible lag time for				±3D	±14D	±14D	±14D	+14D
observation/examination Verify conformance with entry criteria Obtain informed consent	Х							
Patient characteristics	Х							
Serum/urine pregnancy test b	Х	Х						
Patient enrollment		Х						
Administration of the investigational drug		▼						
Pain assessment by patients (VAS)	Х	Х		Х	Х	Х	Х	Х
ODI		Х		Х	Х	Х	Х	Х
Physical examination	Х	Х						
Neurological examination	Х			Х	Х	Х	Х	Х
Imaging (X-ray, MRI) c	Х				Х	Х	Х	Х
Vital signs	Х	Х	Х	Х	Х	Х		Х
Laboratory tests	X			Х	Х	Х		X
Serum anti-SI-6603 antibody d		Х				Х	Х	Х
Concomitant drug/therapy								→ X
AE/SAE								> x
Record occurrence of lumbar surgery e								⇒ X

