#### **Procedures by Visit** 7.2

Visits should occur within the time indicated for each scheduled visit. All times should

<sup>*a* Hospitalization on the day at administration is allowed if it is required by the site.

<sup>b Serum pregnancy test will be performed at Screening, and urine pregnancy test will be performed at *Visit 2 before administration of the investigational drug.* 

<sup>c If repeat imaging is needed, the permissible lag time will be extended by a maximum of an additional 14 days.

<sup>d Examined when considered necessary in unscheduled visit

<sup>e Patients who discontinued the study will be followed until the Week 26 visit.

be recorded using the 24-hour clock (e.g., 23:20, not 11:20 pm).

- 7.2.1 Screening (Visit 1)
  - Obtain written informed consent
  - Record demographic and medical history
  - Record the use of concomitant drug/therapy
  - Document occurrence of lumbar surgery
  - Verify conformance with entry criteria
  - Perform vital signs assessments (temperature, blood pressure, heart and respiration rate)
  - Perform physical examination
  - Perform neurological examination
  - Complete pain assessment (VAS)
  - Perform imaging tests (X-ray and MRI)
  - Obtain study entry laboratory specimens (blood for HIV; pregnancy [for women of childbearing potential]; and hematology, hepatic, and chemistry panels)

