#### 7.2.2 Treatment Day 0 (Visit 2)

The following will be performed on the day of study drug administration (Day 0) before study drug administration:

- Enroll the patient if not done the day before
- Record concomitant drug and therapy information, including drugs or therapy used to treat an AE
- Record AEs and SAEs since previous visit
- Document occurrence of lumbar surgery
- Perform vital sign assessments (temperature, blood pressure, heart and respiration rate)
- Perform physical examination
- Complete pain assessment (VAS) and ODI
- Obtain blood specimen for serum anti-SI-6603 antibody
- Perform urine pregnancy test
- Administration of SI-6603

The following will be done after study drug administration:

Require patients to rest for at least 4 hours. During this resting period the patient's vital signs and general health status will be monitored. After patient monitoring, the Investigator will judge if the patient is ready for discharge based on observation and verification that there are no findings that negatively influence discharging the patient.

- Record concomitant drug and therapy information, including drugs or therapy used to treat an AE
- Record AEs and SAEs

• Perform vital sign assessments (temperature, blood pressure, heart and respiration rate)

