#### Analysis and Data Conventions:

Definition of baseline

For vital signs, laboratory tests, imaging procedures, neurological examinations, and ODI, the last valid assessment made before administration of investigational drug will be used as the baseline for all analyses of that parameter.

For the efficacy parameters of pain assessment measured by VAS, the baseline value of the worst leg pain and back pain over the past 24 hours (VAS) will be the VAS obtained on the day of enrollment (Day -1/Day 0).

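### The only scheduled pre-dose neurological examination is at screening, up to 28 days before the injection, so unnoticed pre-dose change can be read as post-injection change

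*Combined protocol and SAP*

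**What the plan says.** - **Screening.** Section 7.2.1 lists "Perform neurological examination" at Visit 1. Table 3 heads that column "Before 4 Weeks (Day -28 to Day 0"), while Figure 1 ends the window on Day -1. On either reading the visit can fall 28 days before dosing.
- **Day 0.** The pre-dose list in section 7.2.2 includes "Complete pain assessment (VAS) and ODI", vital signs and a physical examination, but no neurological examination. Both Visit 2 cells of the neurological row in Table 3 are blank, and the next mark is at Week 1.
- **Physical examination.** Section 6.1.6 defines it so: "The physical examination should include evaluation of the skin, head, neck, throat, ears, eyes, nose, heart, lungs, abdomen, extremities, and musculoskeletal systems". SLR/FNS, sensation, muscle strength and deep tendon reflexes are not among the items; section 6.1.7 lists them separately as the neurological tests.
- **Baseline.** For neurological examinations, among others, section 8.2 says that "the last valid assessment made before administration of investigational drug will be used as the baseline". For pain VAS it uses the value from the day of enrollment (Day -1 or Day 0).
- **Adverse event rule.** Section 6.1.7 makes reportable "Any neurological finding that worsens after the administration of the investigational drug", provided the investigator considers it clinically significant. It does not name the examination against which worsening is judged.
- **Efficacy.** Sections 3.2.2 and 8.5 make change in neurological status from baseline a secondary endpoint, summarised as the number and percentage of patients with negative tests at each time point.

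**The concern.** The baseline is meant to describe the patient just before the drug. For pain and disability the schedule achieves that: VAS and ODI are both taken pre-dose at Visit 2. For neurological signs it does not. What happens between screening and injection falls inside the interval that is later read as follow-up after treatment.

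The error can go either way. A reflex or sensory change that develops silently during screening is first recorded at Week 1, where it looks like worsening after the injection. A sign that improves before dosing looks like improvement from baseline. For SLR/FNS there is a further reason for caution: inclusion criterion 3 requires a positive test at 70° or less, so the reading that qualifies the patient is also the baseline, and ordinary variation will tend to move later readings in the favourable direction.

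Safety is the primary objective and there is no control group (section 3.3) in which the same drift would show up. Causality under section 6.1.1.3.3 depends partly on timing, and an event counts as related when a causal link cannot be excluded. A sign first recorded after dosing, with no recent pre-dose reading, is hard to classify as unrelated.

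**Working it through.** The plan gives no figure on this point. Its only statistical figures, the exact intervals in section 8.8 for 3 and 15 events in 1000 patients, reproduce (0.062% to 0.874% and 0.842% to 2.462%). They do not enter this check.

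**Step 1: which examination is the baseline?** The neurological row of Table 3 is marked at Visit 1, Weeks 1, 6, 13 and 26, and discontinuation. Section 7.2.2 adds none on Day 0, and the physical examination in 6.1.6 does not include the tests. Under the 8.2 rule the baseline is therefore, by schedule, the screening examination.

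**Step 2: how much of the interval precedes the drug?** Let g be the days from screening to dosing and d the days from dosing to the visit. The pre-dose share is g / (g + d).

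Inputs: g is at most 28 (Figure 1, Table 3). Nominal d is 7, 42, 91 and 182 days, with windows of ±3 days at Week 1 and ±14 days afterwards (Table 3). Screening on Day -14 is an assumed intermediate case; Day -1 is the latest day in Figure 1.

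| Visit | g = 28, nominal | g = 28, across the window | g = 14 | g = 1 |
|---|---|---|---|---|
| Week 1 | 28/35 = 80.0% | 28/38 to 28/32 = 73.7% to 87.5% | 14/21 = 66.7% | 1/8 = 12.5% |
| Week 6 | 28/70 = 40.0% | 28/84 to 28/56 = 33.3% to 50.0% | 14/56 = 25.0% | 1/43 = 2.3% |
| Week 13 | 28/119 = 23.5% | 28/133 to 28/105 = 21.1% to 26.7% | 14/105 = 13.3% | 1/92 = 1.1% |
| Week 26 | 28/210 = 13.3% | 28/224 to 28/196 = 12.5% to 14.3% | 14/196 = 7.1% | 1/183 = 0.5% |

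**Step 3: what would a Day 0 examination change?** With g = 0 the share is zero at every visit. For a patient screened on Day -28, the nominal baseline-to-visit interval falls from 35 to 7 days at Week 1, 70 to 42 at Week 6, 119 to 91 at Week 13 and 210 to 182 at Week 26. The sample size and the 8.8 intervals are unaffected.

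**Step 4: can this be turned into a number of patients?** No. That needs a rate of spontaneous neurological change before dosing, and the documents give none.

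**The case against.** The best case for the plan is that it has other ways to date a pre-dose change.

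- Adverse events are recorded from signing of the consent form (6.1.1.4). Section 7.2.2 requires those since the previous visit to be recorded on Day 0 before dosing, alongside a physical examination that covers the extremities and musculoskeletal system.
- Section 6.1.7 requires clinical significance in the investigator's judgment, so minor drift need not become an adverse event.
- An unscheduled pre-dose neurological examination is not forbidden and would become the baseline under 8.2.
- The efficacy endpoint is secondary and descriptive. The post-dose percentages of negative tests in 8.5 do not themselves use the baseline reading; only the comparison with baseline does.
- Imaging and laboratory baselines also come from screening, so an earlier baseline is not in itself an inconsistency.

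Most of this stands, and it narrows the point. It does not reach a change that the patient does not notice and that questioning and a general physical examination do not reveal. For those, no planned reading separates before from after.

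A reader might infer that all pre-dose change is counted as post-injection change, or that serious deficits cannot be dated. The documents do not support either. The complications described for the predecessor enzyme in section 1.1, and the significant deficits listed in section 9.10, are unlikely to pass unnoticed through the Day 0 assessments.

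A reader might also infer that eligibility must be checked again on Day 0, because "Verify conformance with entry criteria" appears only at Visit 1. That does not follow. The leg-pain threshold in inclusion criterion 6 is tied to the time of consent, and section 4 already makes the investigator responsible for all criteria. A Day 0 recheck would amount to a new rule on who is dosed, and none is proposed here.

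**Conclusion.** The point holds in a limited form. By schedule, the neurological baseline and the only planned comparator for the 6.1.7 rule can be up to 28 days older than the injection. Silent changes in SLR/FNS, sensation, strength or reflexes in that gap can be counted as worsening or improvement after treatment.

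The exposure is greatest at Week 1: 80% of the interval precedes dosing for a patient screened on Day -28, but 12.5% for one screened on Day -1. By Week 26 the largest nominal share is 13%. These percentages are shares of calendar time and should not be read as shares of bias or of misclassified patients.

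The conclusion assumes that sites follow the schedule and add no unscheduled pre-dose examination. The actual distribution of screening days is unknown. A Day 0 examination would remove pre-dose change only; with no control group, natural change after dosing remains mixed with any drug effect. This is a cheap improvement to the baseline, not a flaw that undermines the study.

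**What to change.** In Table 3 and section 7.2.2, add the section 6.1.7 tests (SLR or FNS, sensation, muscle strength, deep tendon reflexes) to the physical examination already scheduled before administration at Visit 2. Name that examination as the neurological baseline in section 8.2 and as the comparator for worsening in section 6.1.7. Keep the screening examination for eligibility, as now.

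The cost is a few minutes of bedside testing per patient, by the same investigator, at a visit that already takes place. It needs no extra visit, staff or invasive procedure. The change has to be made before dosing, because a missing pre-dose reading cannot be recovered later.

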#### 6.1.1.2 Definitions

An AE is any untoward medical occurrence that occurs in a patient or clinical investigation subject administered a pharmaceutical product, and which does not necessarily have a causal relationship with this treatment. An AE can therefore be any unfavorable and unintended sign (including abnormal laboratory finding), symptom, or disease temporally associated with the use of an investigational product, whether or not considered related to the product.

For this study, the following imaging findings will be recorded as AEs:

- Disc height (disc index): decrease in disc height ≥30% compared to baseline value
- Vertebral posterior angle: vertebral body angle formed by flexion of  $\geq 5^{\circ}$
- Vertebral body translation: vertebral body translation of  $\geq 3 \text{ mm}$
- Change in vertebral body endplates and adjacent bone marrow: Type 1, Type 2, or Type 3 change (Modic Classification)

Note: The above events are limited to the targeted level of the procedure and the adjacent vertebral bodies.

All AEs, including intercurrent illnesses, occurring during the study will be documented in the eCRF. Concomitant illnesses, which existed before entry into the study, will not be considered AEs unless they worsen during the treatment period. All AEs, regardless of the source of identification (e.g., physical examination, laboratory assessment, or reported by patient), must be documented.

Pre-existing conditions will be recorded in the eCRF on the Medical History or appropriate page.

A treatment-emergent adverse event will be defined as an AE that begins or that worsens in severity after the study drug has been administered.

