#### 8.2 General Considerations

Categorical variables will be summarized in a contingency table by the number and percentage of patients in each category. Continuous variables will be summarized by the number of observations, mean, standard deviation (SD), median, inter-quartile range, minimum, and maximum. Where data are collected over time, both the observed data and change from the Screening period (baseline) will be summarized at each time point. All eCRFs collected and derived data will be listed.

Methods for imputation of missing data and criteria for inclusion of patients in efficacy analyses will be specified.

All statistical tests will be performed 2-sided with a significance level of 5%, unless otherwise stated.

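### Does calling the pain baseline the Screening period in Section 6.1.7 leave pain adverse events or VAS change without a usable reference?

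*Combined protocol and SAP*

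**What the plan says.** Four parts of the protocol bear on the pain reference.

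- **AE reporting, Section 6.1.7.** The first pain rule covers "Cases where leg pain or back pain increase over the Screening period (baseline value" and also requires the Investigator's judgment of clinical aggravation. A second rule covers exacerbation "based on post treatment improvement followed by the reappearance of pain of equal severity than before improvement". Neither gives a number of millimetres or names a visit.
- **General summaries, Section 8.2, repeated in the Synopsis.** For data collected over time, "both the observed data and change from the Screening period (baseline) will be summarized at each time point".
- **Definition of baseline, Section 8.2 (Analysis and Data Conventions).** Vital signs, laboratory tests, imaging, neurological examination and ODI use the final valid pre-dose measurement. For leg and back pain, described there as efficacy parameters, the baseline "will be the VAS obtained on the day of enrollment (Day -1/Day 0".
- **Schedule.** Section 7.2.1 (Visit 1) lists "Complete pain assessment (VAS" and Section 7.2.2 (Day 0, before dosing) lists "Complete pain assessment (VAS) and ODI". Table 3 in Section 7.1 heads the Visit 1 column "Before 4 Weeks (Day -28 to Day 0", whereas Figure 1 in Section 3.1 ends screening at Day -1.

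**The concern.** Section 6.1.7 treats the Screening period and the baseline as the same thing, while Section 8.2 puts the VAS baseline at the day of enrollment. The schedule does not settle the matter, because Figure 1 and Table 3 disagree on whether Day 0 belongs to screening.

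If a site takes the phrase to mean the Visit 1 score, two things can go wrong. Pain that rose only before the injection can meet the first rule. Pain that had eased by Day 0 and then rose after the injection, but not above its Visit 1 level, does not meet it. The second rule does not cover that patient either, since it needs improvement after treatment first. By contrast, the neurological rule in the same section is tied to worsening after administration.

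The event in question matters. Section 1.3.1.3 names back pain as the most frequent treatment-related AE in past studies, and this trial has no control arm against which uneven reporting would cancel. The VAS displays in Sections 8.6.8 and 8.6.9 also sit among the safety analyses, while the VAS baseline is worded for efficacy parameters.

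**Working it through.** The protocol has no figure of its own on this point. Its only design calculation, the Clopper-Pearson limits in Section 8.8, does reproduce. With lower limit Beta(0.025; x, n-x+1), upper limit Beta(0.975; x+1, n-x) and n = 1000, x = 3 gives 0.062% to 0.874% and x = 15 gives 0.842% to 2.462%. Neither interval depends on the pain baseline. The rest of the check compares the texts.

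**Step 1: does every measure have a defined baseline?** The scheduled pre-dose assessments come from Table 3 and Sections 7.2.1 and 7.2.2.

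| Measure | Scheduled before dosing | Baseline under Section 8.2 | If Screening meant Visit 1 only |
|---|---|---|---|
| Laboratory tests | Visit 1 | last valid pre-dose value | same |
| Imaging | Visit 1 | last valid pre-dose value | same |
| Neurological examination | Visit 1 | last valid pre-dose value | same |
| Vital signs | Visits 1 and 2 | last valid pre-dose value | earlier visit |
| VAS pain | Visits 1 and 2 | day of enrollment | earlier visit |
| ODI | Visit 2 | last valid pre-dose value | no value |

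On the Visit 1 reading, 3 measures agree with Section 8.2, 2 point to an earlier visit and 1 has no value (3 + 2 + 1 = 6). All 6 nevertheless have an explicit rule in Section 8.2, so the disagreement leaves no planned summary undefined.

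**Step 2: is the Visit 1 reading tenable?** The general sentence applies to all data collected over time, which includes ODI. ODI is first collected at Visit 2. The label therefore cannot mean Visit 1 throughout and reads as shorthand for the pre-treatment baseline. Section 6.1.7 adds the word baseline to the same phrase, and the only VAS baseline the protocol defines is the one in Section 8.2. The words about efficacy parameters there describe the variable, since Sections 3.2.2 and 6.2 list VAS pain under efficacy. They do not confine the definition to the tables of Section 8.5.

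**Step 3: can a pain event be lost or misdated?**

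- *Pain that rises between Visit 1 and dosing.* Section 6.1.1.4 records AEs from consent with date and time of onset, and Section 7.2.2 asks for AEs before the injection. The definition of a treatment-emergent event in Section 6.1.1.2 then separates these cases from later ones.
- *Pain that rises after dosing but not above Visit 1.* Section 6.1.7 says which cases meet the reporting criteria. It does not say that others fail. Section 6.1.1.2 counts any unfavorable symptom and requires all AEs to be documented whatever their source. It says that illnesses present before entry "will not be considered AEs unless they worsen during the treatment period", which ties the judgment to the treatment period. Section 6.1.1.1 requires open questioning about how the patient has felt since the previous contact.

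**Step 4: how far apart are the candidate references?** Visit 1 can be as early as Day -28 and dosing is Day 0, so the two scores are at most 0 - (-28) = 28 days apart. Under Section 8.2 the baseline is at most 0 - (-1) = 1 day before dosing.

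**Step 5: can an effect be sized?** Only with inputs from outside the documents. A simulation assumed a mean of 70 mm at both pre-dose scores, SD 15 to 25 mm, correlation 0.5 to 0.9 between them, and correlation 0.4 with the later score. The two references then disagree on whether the score rose in 13% to 32% of patients with no mean change, 6% to 22% with a mean fall of 20 mm, and 0.3% to 7% with a mean fall of 45 mm. The overall proportion with a rise differs by no more than 0.2 percentage points between references, but that follows from assuming equal pre-dose means. These are raw score movements, not AEs, because the rule turns on clinical judgment and has no threshold. They give no estimate of bias.

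**The case for a change.** The strongest argument for a change rests on back pain and on under-reporting. Table 1 in the protocol gives treatment-related back pain in 64/269 = 23.8% of SI-6603 patients against 6/128 = 4.7% on placebo. Section 1.3.1.3 links back pain soon after injection to breakdown of the nucleus pulposus. Early worsening without prior improvement is therefore the case most worth catching, and it is the case that a Visit 1 comparison would not flag. Investigator judgment does not say what to compare with. Section 8.6.1 tabulates AEs without invoking the treatment-emergent definition. Definitions added later in the SAP can restrict tables, but they cannot recover events that sites never reported.

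Part of this stands. The phrase in Section 6.1.7 is loose, Figure 1 and Table 3 differ by a day, and two sites could read the phrase differently. What does not stand is the step to lost events. That would need sites to treat Section 6.1.7 as an exclusive test and set aside the general duty in Sections 6.1.1.1, 6.1.1.2 and 6.1.1.4 to collect and record any worsening. The silence of Section 8.6.1 on treatment emergence affects all AEs, and onset dates allow the separation in analysis.

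Naming the Day 0 pre-dose score in Section 6.1.7 would not fully align the two references either. Section 7.2.2 allows enrollment on the day before dosing, so the Section 8.2 baseline may be a Day -1 score and the one-day difference would remain.

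**Conclusion.** No change to the plan is needed. The inconsistency is real but clerical: one label is used loosely in Section 6.1.7, in the general text of Section 8.2 and in the Synopsis, while Section 8.2 itself supplies the working definition. Analysts would take VAS change, including the displays in Sections 8.6.8 and 8.6.9, from that definition.

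In size, the plan leaves none of the six measures without a baseline rule. The two VAS scores in question are at most 28 days apart. Any effect on pain AE counts cannot be sized or signed from the documents.

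The conclusion assumes that a specific definition governs a general label, that sites apply the general AE rules alongside Section 6.1.7, and that the SAP carries the Section 8.2 baseline forward. Using the Section 8.2 term in all three places would be tidier if those sections were being edited for another reason, but no planned result depends on it.
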